10.2.10 Concomitant Medication at Baseline

Concomitant medication at baseline according to the ATC classification.

Table 10.2.10.1 Concomitant medication at baseline (ATC levels 1, 2 and 4)

	S1 (TR)		S2 (RT)		Total	
	N	%	N	%	N	%
<hr/>						
Alimentary tract and metabolism						
Antacids						
Magnesium compounds						
Magnesium adipate						
...						
Blood and blood forming organs						
Antithrombotic agents						
Vitamin K antagonists						
Acenocoumarol						
...						

Notes: Percentage is based on number of patients in total and by sequence, when applicable.

S1, Sequence 1; S2, Sequence 2; TR, test-reference; RT, reference-test.

11 APPENDIX II: SAFETY ANALYSIS

Safety analysis will be carried out on evaluable patients for the safety population.

11.1 *Extent of exposure*

11.1.1 *Treatment Administration*

Table 11.1.1.1 Number of cycles administered[†]

No. of cycles administered	S1 (TR)		S2 (RT)		Total	
	N	%	N	%	N	%
1 cycle						
2 cycles						
3 cycles						

Notes: Percentage is based on number of patients in total and by sequence, when applicable.

[†] Including when lorbinecetin is administered both alone and in combination with bosentan.

S1, Sequence 1; S2, Sequence 2; TR, test-reference; RT, reference-test.

Table 11.1.1.2 Summary of number of cycles administered[†] and time on treatment

	S1 (TR)	S2 (RT)	Total
No. of cycles administered			
per patient			
N			
Median (range)			
Time on treatment (weeks)*			
N			
Median (range)			

[†] Including when lorbinecetin is administered both alone and in combination with bosentan.

*Time on treatment is defined as the last administration date of lorbinecetin plus 31 days, death or the start date of the new therapy, whichever comes first, minus the first administration date.

S1, Sequence 1; S2, Sequence 2; TR, test-reference; RT, reference-test.

Table 11.1.1.3 Dose information by sequence

	S1 (TR)	S2 (RT)	Total
Lorbinecetin			
Cumulative dose (mg/m ²)			
N			
Median (range)			
Dose intensity (mg/m ² /week)			
N			
Median (range)			
Relative dose intensity (%)			
N			
Median (range)			
Bosentan			
Cumulative dose (mg)			
N			
Median (range)			

S1, Sequence 1; S2, Sequence 2; TR, test-reference; RT, reference-test.

11.1.2 Cycle Delays

Table 11.1.2.1 Summary of lurbinectedin dose delays

	S1 (TR)		S2 (RT)		Total	
	N	%	N	%	N	%
No. of patients treated						
No. of patients susceptible to have dose delay †						
No. of patients with any dose delay						
Drug related‡ AE						
Non-drug related AE						
Other reason						
No. of cycles administered						
No. of cycles susceptible to have dose delay ††						
No. of cycles with any dose delay ‡‡						
Drug related‡ AE						
Non-drug related AE						
Other reason						

† Excluding patients who received only the first cycle.

‡ Related or unknown relationship

†† All cycles excluding first cycle

‡‡ Denominator = Number of cycles susceptible to have dose delay

S1, Sequence 1; S2, Sequence 2; TR, test-reference; RT, reference-test.

Table 11.1.2.2 Length of dosing delay

	S1 (TR)		S2 (RT)		Total	
	N	%	N	%	N	%
Length of delay‡‡						
≤ 7 days						
> 7 to ≤ 14 days						
> 14 days						

‡‡ Denominator = Number of cycles susceptible to have dose delay

S1, Sequence 1; S2, Sequence 2; TR, test-reference; RT, reference-test.

Listing 11.1.2.3 Dose delays

Sequence	Subject	Cycle	Delay (days)	Reason for delay

11.1.3 Dose Reductions

Table 11.1.3.1 Summary of lurbinectedin dose reductions

	S1 (TR)		S2 (RT)		Total	
	N	%	N	%	N	%
No. of patients treated						
No. of patients susceptible to have dose reduction [†]						
No. of patients with any dose reduction						
Drug related [‡] AE						
Non-drug related AE						
Other reason						
No. of cycles administered						
No. of cycles susceptible to have dose reduction ^{††}						
No. of cycles with any dose reduction ^{‡‡}						
Drug related [‡] AE						
Non-drug related AE						
Other reason						

[†] Excluding patients who received only the first cycle.

[‡] Related or unknown relationship

^{††} All cycles excluding first cycle

^{‡‡} Denominator = Number of cycles susceptible to have dose delay/reduction

S1, Sequence 1; S2, Sequence 2; TR, test-reference; RT, reference-test.

Listing 11.1.3.2 Dose reductions

Sequence	Subject	Cycle	Lurbinectedin intended dose (mg/m ²)	Reason for dose reduction	Specify

11.1.4 Any Other Dose Modifications

Listing 11.1.4.1 Dose interruptions for lurbinectedin

Sequence	Subject	Cycle	Date	Reason for interruption	Specify

Listing 11.1.4.2 Dose not taken according to protocol for Bosentan

Sequence	Subject	Cycle	Day	Reason

11.2 Adverse Events (AEs)

Adverse events tables will be listed by total and sequence or differentiating by treatment (Test, Reference or both).

Type of toxicity and worst grade or severity by cycle and by patient will be summarized according to System Organ Class (SOC) and Preferred Term (PT) as per the MedDRA dictionary. Subsequent grouping of similar or clinically related items might be appropriate at the time of the analysis.

Tables will be organized by category of events using SOC and PT. Grades could be presented by separate or any other grouping at the time of the analysis.

11.2.1 Display of Adverse Events

Table 11.2.1.1 Summary of adverse events

	BOS+LRB		LRB alone	
	N	%	N	%
No. of patients with any AE				
No. of patients with any treatment-related [†] AE				
Patients with any grade ≥ 3 AE				
Patients with any grade ≥ 4 AE				
No. of patients with any grade ≥ 3 treatment-related [†] AE				
No. of patients with any grade ≥ 4 treatment-related [†] AE				
No. of patients with any SAE				
No. of patients with any treatment-related [†] SAE				
No. of patients with any grade ≥ 3 SAE				
No. of patients with any grade ≥ 4 SAE				
Any grade ≥ 3 treatment-related [†] SAE				
Any grade ≥ 4 treatment-related [†] SAE				
No. of patients with deaths associated with AEs				
No. of patients with deaths associated with treatment-related [†] AEs				
No. of patients with dose delays associated with AEs				
No. of patients with dose delays associated with treatment-related [†] AEs				
No. of patients with dose reductions associated with AEs				
No. of patients with dose reductions associated with treatment-related [†] AEs				
No. of patients with AEs leading to treatment discontinuation				
No. of patients with treatment-related [†] AEs leading to treatment discontinuation				

[†] Related to combination, lirbinezdin or bosentan, or with unknown relationship

Number of patients with at least one event, treatment modification, withdrawal or death during the treatment with BOS+LRB or LRB alone.

BOS, bosentan; LRB, lirbinezdin.

Table 11.2.1.2 Treatment Related[†] (or with unknown relationship) Adverse Events. Worst grade per treatment

SOC/PT	BOS+LRB						LRB alone					
	All grades		Gr ≥ 3		Gr ≥ 4		All grades		Gr ≥ 3		Gr ≥ 4	
	N	%	N	%	N	%	N	%	N	%	N	%
...												

Notes: Percentage is based on number of patients by treatment, when applicable.

[†] Related to both or lorbinectedin or bosentan or with unknown relationship

BOS, bosentan; LRB, lorbinectedin.

Table 11.2.1.3 Lorbinectedin related[†] Adverse Events. Worst grade per treatment

SOC/PT	BOS+LRB						LRB alone					
	All grades		Gr ≥ 3		Gr ≥ 4		All grades		Gr ≥ 3		Gr ≥ 4	
	N	%	N	%	N	%	N	%	N	%	N	%
...												

Notes: Percentage is based on number of patients by treatment, when applicable.

[†] Related to lorbinectedin or with unknown relationship

BOS, bosentan; LRB, lorbinectedin.

Table 11.2.1.4 Bosentan related Adverse Events. Worst grade per treatment

SOC/PT	BOS+LRB					
	All grades		Gr ≥ 3		Gr ≥ 4	
	N	%	N	%	N	%
...						

Notes: Percentage is based on number of patients by treatment, when applicable.

[†] Related to bosentan or with unknown relationship

BOS, bosentan; LRB, lorbinectedin.

Table 11.2.1.5 Treatment Related[†] (or with unknown relationship) Adverse Events. Worst grade per patient

SOC/PT	S1 (TR)						S2 (RT)						Total					
	All grades		Gr ≥ 3		Gr ≥ 4		All grades		Gr ≥ 3		Gr ≥ 4		All grades		Gr ≥ 3		Gr ≥ 4	
	N	%	N	%	N	%	N	%	N	%	N	%	N	%	N	%	N	%
...																		

Notes: Percentage is based on number of patients in total and by sequence, when applicable.

[†] Related to both or lorbinectedin or bosentan or with unknown relationship

S1, Sequence 1; S2, Sequence 2; TR, test-reference; RT, reference-test.

Table 11.2.1.6 Adverse Events regardless of relationship. Worst grade per treatment

SOC/PT	BOS+LRB						LRB alone					
	All grades		Gr ≥ 3		Gr ≥ 4		All grades		Gr ≥ 3		Gr ≥ 4	
	N	%	N	%	N	%	N	%	N	%	N	%
...												

Notes: Percentage is based on number of patients by treatment, when applicable.

BOS, bosentan; LRB, lorbinectedin.

Table 11.2.1.7 Adverse Events regardless of relationship. Worst grade per patient

SOC/PT	S1 (TR)				S2 (RT)				Total			
	All grades		Gr ≥ 3	Gr ≥ 4	All grades		Gr ≥ 3	Gr ≥ 4	All grades		Gr ≥ 3	Gr ≥ 4
	N	%	N	%	N	%	N	%	N	%	N	%
...												

Notes: Percentage is based on number of patients in total and by sequence, when applicable.

S1, Sequence 1; S2, Sequence 2; TR, test-reference; RT, reference-test.

Listing 11.2.1.8 AEs grade ≥ 3

Sequence	Treatment	Cycle	Subject	SOC	PT	Grade	SAE	Start	End	Relationship	Action	Serious	Outcome
							(Y/N)	date	date	study		Event	medication

[†]BOS+LRB/LRB alone

Listing 11.2.1.9 AEs related only to lurbinectedin

Sequence	Treatment	Cycle	Subject	SOC	PT	Grade	SAE	Start	End	Action	Serious	Outcome
							(Y/N)	date	date	taken	Event	

[†]BOS+LRB/LRB alone

Listing 11.2.1.10 AEs related only to bosentan

Sequence	Treatment	Cycle	Subject	SOC	PT	Grade	SAE	Start	End	Action	Serious	Outcome
							(Y/N)	date	date	taken	Event	

[†]BOS+LRB

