2 OVERALL STUDY DESIGN

This is a prospective, open-label, two-way crossover, phase Ib drug-drug interaction study in patients with advanced solid tumors.

The study will include a pre-treatment (screening) phase (within 14 days before the first lurbinectedin or bosentan administration) followed by a treatment phase consisting of two lurbinectedin cycles, one cycle in combination with bosentan and one cycle of lurbinectedin as single agent (in different order depending on the study sequence), and one additional third cycle of lurbinectedin as a single agent for patients who meet the continuation criteria and obtain a clinical benefit after the first two cycles, and then follow-up of adverse events if any.

Patients who meet the continuation criteria and obtain a clinical benefit according to the Investigator's criteria will have the opportunity to continue treatment under a Compassionate Use Agreement after the completion of the optional third study cycle.

Patients will be treated as outpatients. At the discretion of the Investigator, patients may be admitted to the study center on Day -1 or Day 1 and monitored, at least, until completion of the Day 1 PK blood sample collections.

[figure not shown]
Patients will receive a maximum of three cycles: two consecutive cycles of lurbinecetin, one cycle with and one cycle without bosentan co-administration (in different order depending on the study Sequence 1 or Sequence 2 of treatment), followed by a third cycle with lurbinecetin alone (this last optional for patients with clinical benefit). Lurbinecetin will be administered as a 1-hour (-5/+20 min) i.v. infusion every three weeks (q3wk) via a central or peripheral vein.

In the co-administration cycles, bosentan will be administered orally twice daily in the morning and evening during the prior five consecutive days, self-administered at home from Day -5 to Day -1 (i.e., five days before lurbinecetin infusion), and once daily on Day 1 (i.e., the day of lurbinecetin infusion), following recommendations at the Summary of Product Characteristics (SmPC). On Day 1 (i.e., the day of lurbinecetin infusion), bosentan will be given immediately prior to starting the lurbinecetin infusion. In fact, bosentan should be administered after obtaining the bosentan PK sample #1 and before the start of lurbinecetin infusion (-15 min to -1 min).

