Patients will receive lorbinecetin until disease progression, unacceptable toxicity, consent withdrawal or while it is considered to be in their best interest, and for a maximum of three cycles. Treatment with lorbinecetin outside this study could be continued under a Compassionate Use Agreement after the completion of the optional third study cycle.

All patients will be randomly assigned to the corresponding sequences:

- Sequence 1 (TR):
 - Cycle 1: Bosentan + lorbinecetin
 - Cycle 2: Lorbinecetin alone
 - Cycle 3: Lorbinecetin alone (optional)

- Sequence 2 (RT):
 - Cycle 1: Lorbinecetin alone
 - Cycle 2: Bosentan + lorbinecetin
 - Cycle 3: Lorbinecetin alone (optional)

Lorbinecetin will be administered to eight evaluable patients and for a maximum of three cycles, while considered to be on the patient's best interest or until progressive disease (PD), unacceptable toxicity, intercurrent illness of sufficient magnitude to preclude safe continuation of the study, patient's refusal and/or non-compliance with study requirements, a protocol deviation with an effect on the risk/benefit ratio of the clinical study or any other reason at the physician's judgment that precludes lorbinecetin continuation.

If the patient responds to treatment after the first two cycles according to Investigator criteria for clinical benefit, treatment with lorbinecetin may continue outside this study under a Compassionate Use Agreement at the same dose based on Investigator's decision and upon agreement with the Sponsor. Then, the treating center must request authorization to the relevant Health Authorities and notify the Sponsor in due time. In order to avoid a treatment discontinuation, during the Compassionate Use Agreement authorization an additional third cycle with lorbinecetin is allowed.

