4 OBJECTIVES AND ENDPOINTS

4.1 *Objectives*

This clinical pharmacology study is designed to assess the impact of bosentan co-administration on lorbinecetin PK parameters administered alone.

4.1.1 *Primary Objective*

- To assess the effect of bosentan on lorbinecetin total plasma exposure in patients with advanced solid tumors.

4.1.2 *Secondary Objective*

- To assess the effect of bosentan on lorbinecetin unbound plasma exposure.
- To assess the effect of bosentan on lorbinecetin major metabolites (i.e., M1 and M4).
- To assess the effect of bosentan on the safety profile of lorbinecetin.
- To collect and store a blood sample for germline DNA extraction for future pharmacogenetic (PGt) analysis of variations on genes that may influence exposure and response (i.e., disposition, metabolism and safety) to lorbinecetin.

4.2 *Endpoints*

4.2.1 *Primary Endpoint*

- Plasma dose-normalized C_{max} and $AUC_{0-\infty}$ of lorbinecetin will be compared between Cycle 1 and Cycle 2. Pharmacokinetic analyses will be evaluated in plasma by standard non-compartmental methods, or population methods, if necessary.

4.2.2 *Secondary Endpoint*

- Differences in dose-normalized total AUC_{0-t} and C_{max} and in Cl , Volume of Distribution at Steady State (V_{ss}) and $T_{1/2}$ of lorbinecetin between Cycle 1 and Cycle 2 will be explored.
- Differences in dose-normalized unbound $AUC_{u,0-\infty}$, $AUC_{u,0-t}$ and $C_{u,max}$ and in CL_u , $V_{ss,u}$ and $T_{1/2,u}$ of lorbinecetin between Cycle 1 and Cycle 2 will be explored.
- Differences in ratios between total $AUC_{0-\infty}$, AUC_{0-t} and C_{max} , of main lorbinecetin metabolites relative to parent drug between Cycle 1 and Cycle 2 will be explored. Additional PK parameters will be calculated if deemed appropriate.
- Treatment safety, including AEs, serious adverse events (SAEs) and laboratory abnormalities will be graded according to the NCI-CTCAE v.5. Additionally, treatment compliance, in particular dose reductions requirements and/or treatment delays due to AEs, and reasons for treatment discontinuation will also be described. Patients will be evaluable for safety if they have received at least one partial or complete infusion of lorbinecetin.

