6 STATISTICAL METHODOLOGY

The PK definitions and analysis plan will be described by the Clinical Pharmacology department in a separate document. The present Statistical Analysis Plan (SAP) is focused on the statistical methodology for safety.

Safety analyses will consider treatment emergent AEs and SAEs, according to their relationship with study treatment, as well as analytical results, deaths and the reasons for treatment discontinuations, delays and/or dose reductions.

All AEs and SAEs will be coded using the Medical Dictionary for Regulatory Activities (MedDRA).

Descriptive statistics will be used to characterize the profiles of drug-related AEs, drug-related deaths, SAEs, clinical laboratory data, drug-related delays and/or treatment discontinuations. Tables will be displayed by sequence and treatment (Sequence 1 [TR] vs. Sequence 2 [RT]) and treatment group (Test [lurbinectedin administered in combination with bosentan] vs. Reference [lurbinectedin alone]) .

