Safety analysis will be done by sequence (Sequence 1 [TR] vs Sequence 2 [RT]) and treatment group (Test [lurbinectedin administered in combination with bosentan] vs Reference [lurbinectedin alone]). Additional groups could be done (such a dose level in case dose of lurbinectedin was adjusted) if required, and a sequential number will be added at the end of the table number to differentiate them within each section.

No other subgroup analysis is planned.

7.7 *Pharmacogenetics Analyses*

The analysis will be detailed and reported in a separate document.

7.8 *Decimal places*

By default, all results will be rounded to one decimal, except when variables are integers; in that case, they will be reported without decimals, (e.g. age in years or number of sites).

7.9 *Imputation in Incomplete Dates*

The dates of certain historical or current clinical activities are key component for statistical analysis. An incomplete date results from a missing day, month or year; in that case, the missing figure can be imputed allowing for the calculation of variables, such duration and time to certain event. However, when all of them, day, month and year, are missing no imputation will be done.

Before randomization/treatment start date

All variables needed to summarize for example prior information (e.g. first diagnosis date) where partial information is available will be subject of imputation by means of SAS programming. If the day of a date is unknown then the imputed day will be 1, if the month is also unknown then the imputed date will 1/July. This assumption will be valid if the imputed date is earlier than the randomization date; otherwise, the imputed date will be the first day of the month of the randomization date (i.e. 01/Randomization month date/year).

Between treatment start and end of treatment

All date variables during treatment where information is needed and is not fully available, for example adverse events or concomitant medications, will be subject of imputation by means of SAS programming. If the day of a date is unknown then the imputed day will be 1, if the month and/or year is also unknown then the imputed date will be 1/January (this assumption will be valid if the imputed date is not earlier than the treatment start date; otherwise, the imputed date will be the treatment start date).

After end of treatment

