	All grades		Gr ≥ 3		Gr ≥ 4		All grades		Gr ≥ 3		Gr ≥ 4	
	N	%	N	%	N	%	N	%	N	%	N	%
...												

Notes: Percentage is based on number of patients by treatment, when applicable.
BOS, bosentan; LRB, lorbinecetin..

Table 11.3.1.6 SAEs regardless of relationship. Worst grade per patient

SOC/PT	S1 (TR)						S2 (RT)						Total					
	All		Gr ≥ 3		Gr ≥ 4		All		Gr ≥ 3		Gr ≥ 4		All		Gr ≥ 3		Gr ≥ 4	
	grades	N	%	N	%	N	%	N	%	N	%	N	%	N	%	N	%	
...																		

Notes: Percentage is based on number of patients in total and by sequence, when applicable.
S1, Sequence 1; S2, Sequence 2; TR, test-reference; RT, reference-test.

Listing 11.3.1.7 All SAEs[†]

Sequence	Treatment	Cycle	Subject	SOC	PT	Grade	AE	AE	AE	Start	End date
						status	Relationship	consequences			
group*											

[†]SAE narratives will be provided by the pharmacovigilance department

*BOS+LRB/LRB alone

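### The by-treatment safety tables do not stop at Cycle 2, so on the SAP's definitions optional Cycle 3 counts as lurbinectedin alone and one combination cycle is compared with up to two single-agent cycles.

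*SAP*

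**What the plan says.** SAP Section 4.1.2 lists a secondary objective that begins "To assess the effect of bosentan on the safety profile of" lurbinectedin. SAP Sections 6 and 7.6 define the two safety comparison groups by regimen alone: Test is lurbinectedin with bosentan, Reference is lurbinectedin alone. Neither mentions cycles.

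SAP Section 2 gives each patient one cycle of each regimen in Cycles 1 and 2, in randomized order. It then allows "one additional third cycle of lurbinectedin as a single agent for patients who meet the continuation criteria and obtain a clinical benefit". Cycle 3 carries the same lurbinectedin-alone label in both sequences.

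The note under Table 11.2.1.1 states the counting rule: "Number of patients with at least one event, treatment modification, withdrawal or death during the treatment with BOS+LRB or LRB alone". The related tables report worst grade per treatment, with patients as the denominator. The treatment key of Listing 11.3.1.7 (all SAEs) has only two values, "BOS+LRB/LRB alone".

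The safety population in SAP Section 3 is every patient with at least one lurbinectedin dose. The two-cycle condition in that section belongs to PK evaluability.

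**The concern.** A crossover comparison of safety is fair when each patient is observed for the same number of cycles on each regimen. Here a patient who takes Cycle 3 has one cycle in the BOS+LRB column and two in the LRB-alone column. The measures are any event per patient and worst grade per patient. Neither can fall when a cycle is added, and neither is adjusted for cycles or time at risk.

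The imbalance works in one direction only: it raises the Reference column and makes the combination look less toxic. The extra cycle also comes from a selected group, namely patients who benefited and met the continuation criteria. What is at stake is the by-treatment comparison that serves a stated secondary objective.

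**Working it through.** **Which column Cycle 3 falls in.** No sentence in the SAP says. Three do so in combination: Reference means lurbinectedin alone (Sections 6 and 7.6), Cycle 3 is lurbinectedin alone (Section 2), and any event during treatment with a regimen counts for that regimen (Table 11.2.1.1). Cycle 3 data are in scope, because safety monitoring runs to 31 (±10) days after the last infusion and Table 11.1.1.1 has a row for three cycles.

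**Cycles and days per patient.** BOS+LRB: 1 cycle. LRB alone: 1 cycle without Cycle 3, 2 with it. Ignoring delays and the bosentan lead-in, nominal observation for a Cycle 3 patient is 21 days on BOS+LRB and 21 + 31 = 52 days on LRB alone.

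**Effect on a rate with no bosentan effect.** The plan states no figure for these tables, so there is none to reproduce. Let p be the per-cycle event probability and f the share entering Cycle 3, with independent cycles of equal risk. The BOS+LRB rate is p. The LRB-alone rate is (1−f)p + f[1−(1−p)²] = p + f·p(1−p).

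Protocol Section 1.1.3.5 gives modelled first-cycle grade 3/4 rates of about 69% (neutropenia) and 13% (thrombocytopenia) at stated baseline counts. The 40% rate and all values of f are assumptions.

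| p | f = 25% | f = 50% | f = 100% |
|---|---|---|---|
| 13% | 15.8% | 18.7% | 24.3% |
| 40% | 46% | 52% | 64% |
| 69% | 74.4% | 79.7% | 90.4% |

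For example, 0.13 + 0.5 × 0.13 × 0.87 = 0.187, and 0.69 + 0.5 × 0.69 × 0.31 = 0.797.

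**Effect in 8 patients.** Take p = 40% and 4 patients entering Cycle 3. With independent cycles the mean excess in the LRB-alone count is 4 × 0.4 × 0.6 = 0.96 patients. Correlation within patients is represented by a logit random intercept with SD 2, holding the marginal rate at 40%. The chance of any event in two cycles is then 54.6%, and the mean excess is 4 × (0.546 − 0.400) = 0.59 with rounding. The distribution of the difference in counts is the convolution of the eight patients' individual differences.

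| Scenario | LRB alone higher / lower | Gap of at least 2 patients, LRB alone higher / lower | Mean excess |
|---|---|---|---|
| Cycles 1-2 only, independent | 40% / 40% | 22% / 22% | 0 |
| Cycle 3 in, independent | 60% / 23% | 40% / 10% | 0.96 |
| Cycle 3 in, correlated | 52% / 23% | 27% / 8% | 0.59 |
| Cycle 3 in, correlated, Cycle 3 risk halved | 44% / 30% | 21% / 12% | 0.29 |

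With complete dependence between a patient's cycles there is no shift.

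**Laboratory tables.** Protocol Table 5 schedules Cycle 3 hematology and biochemistry on Day 1 only. SAP Section 6.2 maps end-of-treatment laboratory results to the last cycle, so Cycle 3 still contributes something. However, SAP Section 1 puts the myelosuppression nadir in the middle of the second week, which those visits largely miss. The 13% and 69% rows therefore sit at the upper end.

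**The case against.** The strongest reply is that this is an unstated convention rather than a stated error. The design is a two-way crossover, TR and RT name two periods, and a programmer could leave Cycle 3 out without contradicting any sentence. That is fair as far as it goes: a reader might infer that the SAP expressly assigns Cycle 3 to the LRB-alone column, and it does not. But no rule excludes Cycle 3 either, and the written counting rule includes it.

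It can also be said that Cycle 3 events are traceable. SAP Section 11.2 provides for worst grade by cycle, Listings 11.4.1.5 and 11.4.2.5 are by cycle, the AE listings carry a cycle column, and Section 7.6 allows extra groups if required. This helps a careful reader, but it does not correct the two table columns.

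The limits on size stand: the tables are descriptive, about eight patients are involved, uptake is unknown, and correlation or a lower Cycle 3 risk shrinks the excess.

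Two stronger readings are not supported:
- A reader might infer that the protocol predicts shorter exposure with bosentan, so that the artefact would pass as induction. Protocol Section 3.2 gives only lower bounds for measurable concentrations (at least 80 hours with bosentan, at least 160 without), which do not establish that.
- A reader might infer that delays and reductions are left unallocated. The Table 11.2.1.1 note already counts treatment modifications under the treatment during which they occur.

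**Conclusion.** The concern holds. Followed as written, the by-treatment safety tables compare one BOS+LRB cycle with up to two LRB-alone cycles, and any resulting shift favors the combination. The placement of Cycle 3 is an inference from three definitions, but no text in the SAP points the other way.

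The size cannot be fixed from the documents. At an assumed 40% rate with 4 of 8 patients entering Cycle 3, the mean excess in the LRB-alone count is about 0.3 to 1.0 patients across the scenarios shown; it is zero under complete dependence. The move from 13% and 69% to about 19% and 80% assumes half enter Cycle 3, with independent and equal risk.

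A reader might go further and expect a large or certain distortion. The documents do not support that, because they give neither the uptake nor the within-patient correlation. The PK comparison is not affected: lurbinectedin PK is sampled in Cycles 1 and 2 only.

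**What to change.** State in SAP Sections 6 and 7.6 that every BOS+LRB versus LRB-alone safety table uses Cycles 1-2 only, and show Cycle 3 events separately. The tables concerned are 11.2.1.1 to 11.2.1.3, 11.2.1.6, 11.3.1.1, 11.3.1.2, 11.3.1.5, 11.4.1.1, 11.4.2.1, 11.4.3.2, 11.4.3.4, 11.7.1.1 and 11.7.1.2. Tables 11.2.1.4 and 11.3.1.3 have only a BOS+LRB column and need no change. Apply the same limit to the Section 11.5 comparison if it is run.

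The cost is SAP wording and table programming. Cycle 3 events leave the by-treatment comparison but stay in the per-sequence tables and the listings.

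There is one side effect in Section 11.5. On Cycles 1-2 with 4 patients per sequence, treatment, period and sequence saturate the four cells. The SAP names no link; under a logit link, a cell with 0/4 or 4/4 events leaves no finite treatment estimate. With equal, independent risk the chance of such a cell is 1 − [1 − (1−p)⁴ − p⁴]⁴, which is 41%, 49% and 88% at rates of 50%, 40% and 20%. Report paired counts there (both cycles, Test only, Reference only, neither) instead of relying on the model p-value. Little is lost: with 8 pairs, an exact two-sided paired test falls below 0.05 only with at least 6 discordant pairs, all in one direction (6-0 gives 2 × 0.5⁶ = 0.031; 5-0 gives 0.0625; 7-1 gives 0.070).
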